13.2 Appendix 2: Tuberculosis screening flowchart

The subject will not be eligible for randomization if "active tuberculosis is present "or if "latent tuberculosis is present and is untreated as per local guidelines."

* If the first QuantiFERON® TB-Gold In-Tube test (QFT) is indeterminate, the investigator may choose to perform a second QFT or refer the subject for tuberculosis workup per local guidelines.

** If the result of any QFT is "positive" or the results of 2 sequential QFTs are "indeterminate", the subject must be referred to have a tuberculosis workup per local guidelines (if no workup within 12 weeks prior to randomization is available).

13.3 Appendix 3: Psoriasis Area and Severity Index (PASI) and Body Surface Area (BSA)

Body Region	Erythema (E)	Thickening (I) (plaque elevation, induration)	Scaling (D) (desquamation)	True Area % (covered by lesions)
Head and Neck (H)	 None (0)  Slight (1)  Moderate (2)  Severe (3)  Very severe (4)	 None (0)  Slight (1)  Moderate (2)  Severe (3)  Very severe (4)	 None (0)  Slight (1)  Moderate (2)  Severe (3)  Very severe (4)	Record % (0-100) _____ %
Trunk, Axillae and Groin (T)	 None (0)  Slight (1)  Moderate (2)  Severe (3)  Very severe (4)	 None (0)  Slight (1)  Moderate (2)  Severe (3)  Very severe (4)	 None (0)  Slight (1)  Moderate (2)  Severe (3)  Very severe (4)	Record % (0-100) _____ %
Upper Limbs (U)	 None (0)  Slight (1)  Moderate (2)  Severe (3)  Very severe (4)	 None (0)  Slight (1)  Moderate (2)  Severe (3)  Very severe (4)	 None (0)  Slight (1)  Moderate (2)  Severe (3)  Very severe (4)	Record % (0-100) _____ %
Lower Limbs and Buttocks (L)	 None (0)  Slight (1)  Moderate (2)  Severe (3)  Very severe (4)	 None (0)  Slight (1)  Moderate (2)  Severe (3)  Very severe (4)	 None (0)  Slight (1)  Moderate (2)  Severe (3)  Very severe (4)	Record % (0-100) _____ %

13.4 Appendix 4: Investigator's Global Assessment (IGA mod 2011)

Score	Detailed description
0 = Clear	No signs of psoriasis. Post inflammatory hyperpigmentation may be present
1 = Almost clear	Normal to pink coloration of lesions; no thickening; no to minimal focal scaling
2 = Mild disease	Pink to light red coloration; just detectable to mild thickening; predominantly fine scaling
3 = Moderate disease	Dull bright red, clearly distinguishable erythema; clearly distinguishable to moderate thickening; moderate scaling
4 = Severe disease	Bright to deep dark red coloration; severe thickening with hard edges; severe/coarse scaling covering almost all or all lesions

13.5 Appendix 5: Dermatology Life Quality Index (DLQI)

DERMATOLOGY LIFE QUALITY INDEX (DLQI)			
The aim of this questionnaire is to measure how much your skin problem has affected your life OVER THE LAST WEEK. Please check one box for each question.			
1.	Over the last week, how itchy, sore, painful or stinging has your skin been?	Very much A lot A little Not at all	   
2.	Over the last week, how embarrassed or self conscious have you been because of your skin?	Very much A lot A little Not at all	   
3.	Over the last week, how much has your skin interfered with you going shopping or looking after your home or yard?	Very much A lot A little Not at all	    Not relevant 
4.	Over the last week, how much has your skin influenced the clothes you wear?	Very much A lot A little Not at all	    Not relevant 
5.	Over the last week, how much has your skin affected any social or leisure activities?	Very much A lot A little Not at all	    Not relevant 

6.	Over the last week, how much has your skin made it difficult for you to do any sport?	Very much A lot A little Not at all	   	Not relevant 
7.	Over the last week, has your skin prevented you from working or studying?	Yes No	 	Not relevant 
	If "No", over the last week how much has your skin been a problem at work or studying?	A lot A little Not at all	  	
8.	Over the last week, how much has your skin created problems with your partner or any of your close friends or relatives?	Very much A lot A little Not at all	   	Not relevant 
9.	Over the last week, how much has your skin caused any sexual difficulties?	Very much A lot A little Not at all	   	Not relevant 
10.	Over the last week, how much of a problem has the treatment for your skin been, for example by making your home messy, or by taking up time?	Very much A lot A little Not at all	   	Not relevant 

Please check you have answered EVERY question. Thank you.
 
© AY Finlay, GK Khan, April 1992. This must not be copied without the permission of the authors.

**Document History – Changes compared to previous final version of SAP**

Date	Time point	Reason for update	Outcome for update	Section and title impacted (Current)
09.02.2016	Prior to DBL		SAP first version 1.0 is created	Final version 1.0
20.06.2016	Prior to DBL	To keep consistency with latest protocol version	Family history of cardiovascular disease is added in page 12 In addition: 2) PASI and IGA response are changed to PASI and IGA score in page 12	Section 2.3.3 Section 2.3.3
			ii) SAS code is updated in page 24	Section 5.4.1
			iii) Correction of typos	Section 5.5
			iv) Protocol deviation list is updated	Section 2.1.1
16.5.2017	Prior to DBL	To keep consistency with standard analysis/ Master Analysis Plan	Addition of day of last dose of randomized study treatment	Section 2.4.1
			Elaboration of duration of exposure and addition of visit window	Section 2.4.2
			Re-modified the definition of Prior and concomitant medication	Section 2.7.3
			Elaboration of handling of missing data and remodified the definition, as per protocol, of non-responder imputation	Section 2.8
			Overall safety analysis specification	Section 2.7.2 and Section 4
29.5.2017	Prior to DBL	As discussed in Dry-run meeting with CTT	Cardiometabolic biomarker data will additionally be analyzed using stratified Wilcoxon rank sum test if the data does not satisfy normality condition	Section 2.8.4.2
			One correction is made in notable criteria for pulse rate	
			Spelling and format correction	
10.08.2017	Prior to DBL	As discussed with CTT	Visit window for target to background ratio and cardiometabolic biomarker data	Section 2.4.1.1
11.08.2017	Prior to	As discussed with CTT	Visit windows are updated	Section 2.4.1.1

Date	Time point	Reason for update	Outcome for update	Section and title impacted (Current)
	DBL			

---

**List of abbreviations**

AE	Adverse event
ANCOVA	Analysis of covariance
BSA	Body Surface Area
CMB	Cardio metabolic biomarker
CSR	Clinical Study Report
DLQI	Dermatology Life Quality Index
eCRF	Electronic Case Report Form
FAS	Full Analysis Set
FDG-PET/CT	[18F]-fluorodeoxyglucose positron emission tomography with computer assisted tomography
GCP	Good Clinical Practice
HDL	high-density lipoprotein
HIV	human immunodeficiency virus
ICH	International Conference on Harmonization of Technical Requirements for Registration of Pharmaceuticals for Human Use
IGA mod 2011	Novartis Investigator's Global Assessment modified 2011
IL	Interleukin
IRT	Interactive Response Technology
LLN	Lower Limit of Normal
LOCF	Last-observation-carried-forward
MedDRA	Medical Dictionary for Drug Regulatory Affairs
PASI	Psoriasis Area and Severity Index
PFS	prefilled syringe
PK	Pharmacokinetics
PRO	Patient-reported Outcomes
RAN	Randomized Set
SAF	Safety set
SAP	Statistical Analysis Plan
SAS	Statistical Analysis Software
SOC	System Organ Class
s.c	Subcutaneous
TB	Tuberculosis
TBR	Target to background ratio
ULN	Upper Limit of Normal

# 1 Introduction

This statistical analysis plan (SAP) describes the statistical methodologies, which will be used in the phase IV clinical trial (CAIN457AUS02). This is a randomized, double blind, placebo- controlled, parallel group, multicenter study in adult subjects with moderate to severe chronic plaque-type psoriasis in the United States.

The purpose of this study is to evaluate the effect of secukinumab compared to placebo on aortic vascular inflammation and cardiometabolic biomarkers after 12 weeks of treatment, in subjects with moderate to severe plaque-type psoriasis. In addition, this study will evaluate the effect of longer-term treatment with secukinumab (up to 52 weeks) on aortic vascular inflammation.

## 1.1 Study design

In this study, there are four periods:

**Screening:** The screening period is between Week -4 to Baseline (B) visit, the duration of screening period will be up to four weeks (28 days).

[figure not shown]
**Double-blind Treatment Period:** The double-blind treatment period is defined as Randomization through Week 12 (prior to Week 12 dose), which is a total of 12 weeks time.

**Double-blind Induction Period:** The double-blind induction period is defined as the Week 12 dose through Week 15 dose, which is a total of 4 weeks time.

**Open-label Treatment Period:** The open-label treatment period is defined as the Week 16 through Week 52, which is a total of 36 weeks time.

Note: Baseline visit is Week 0 (Visit 2).

A schematic of the study design and visits is presented in figure below:

For more details, see [study protocol](#), Section 3.1

All doses of study treatment will be self-administered. Self-administration of the study treatment refers to subject self-injection or injection by a trained caregiver regardless of whether self-administration occurs at the study site or at home.

Approximately 84 subjects with moderate to severe chronic plaque -type psoriasis will be randomized from approximately 10 investigative sites in the United States. Assuming a 20% screen failure rate, 105 subjects will need to be screened to provide the targeted number of randomized subjects. Subjects who drop out after they have been randomized will not be replaced.

At the start of the Double-blind Treatment Period, eligible subjects will be randomized via Interactive Response Technology (IRT) in a 1:1 ratio to one of two treatment groups (secukinumab 300 mg or placebo).

Assessments for the primary efficacy variable will be performed at Week 12 for both treatment groups prior to subjects receiving their Week 12 dose.

Primary analysis at Week 12 will be considered as the interim analysis. As Week 12 is the primary analysis time point, no adjustment to the significance level of 0.05 will be made.

## **1.2 Study objectives**

### **Primary objective**

[figure not shown]
The primary objective is to evaluate the effect of secukinumab 300 mg s.c. compared to placebo on aortic vascular inflammation with respect to the change from baseline in the target (arterial vascular uptake) to background (venous blood pool) ratio from the aorta. The primary analysis time point will be at Week 12.

### **Secondary objectives**

- To evaluate the effect of secukinumab compared to placebo with respect to change from baseline in cardio metabolic biomarkers (cardio metabolic function [lipid particle size, HDL function (cholesterol efflux)], measures of inflammation [TNF-Alpha, IL-6, C reactive protein, GlycA], adiposity [leptin and adiponectin], insulin resistance [insulin levels/glucose to yield HOMA-IR], and markers predictive of diabetes [apolipoprotein B, ferritin, IL-2 receptor A, IL-18, and fetuin-A]) at Week 12
- To evaluate the effect of secukinumab compared to placebo in subjects with moderate to severe chronic plaque-type psoriasis with respect to change from baseline in the PASI 75, 90 and 100 response rates at Week 12
- To evaluate the effect of secukinumab compared to placebo in subjects with moderate to severe chronic plaque-type psoriasis with respect to the Investigator's Global Assessment mod 2011 (IGA mod 2011) 0 or 1 response at Week 12
- To evaluate the effects of secukinumab compared to placebo with respect to change from baseline in the Dermatology Life Quality Index (DLQI) total score at Week 12

- To evaluate the clinical safety and tolerability of secukinumab as assessed by vital signs, clinical laboratory variables, and adverse event monitoring.

## **2 Statistical methods**

### **2.1 Data analysis general information**

Novartis Business Services will perform the statistical analysis.

Data will be analyzed by the statistical software SAS, Version 9.4 according to Section 9 (Data Analysis) of the study protocol which will also be available in Appendix 16.1.1 of the Clinical Study Report (CSR). Important information is given in the following sections and details are provided, as applicable, which will also be in Appendix 16.1.9 of the CSR.

At the Week 12 primary analysis time point, only the independent statistician and programmer(s) from Novartis will be unblinded in order to perform the interim analysis. The same SAP will be used for interim analysis.

It is planned that the data from all centers that participate in this protocol will be combined, so that an adequate number of subjects will be available for analysis.

Unless otherwise specified, all statistical tests will be conducted against a two-sided alternative hypothesis, employing a significance level of 0.05.

Efficacy, safety, and other data will be summarized as follows:

- for continuous variables, descriptive summary statistics (number of subjects, mean, standard deviation, median, 25th and 75th percentiles, interquartile range, minimum, and maximum) at each time point and for change from baseline to each visit will be reported by treatment group.

- for categorical variables, frequency and percentage will be presented at each time point by treatment group. Percentages will be calculated with respect to the number of subjects by treatment in the analysis set of interest.

## 2.1.1 General definitions

### 2.1.1.1 Study treatment

Secukinumab 300 mg (two s.c. injections of the secukinumab 150 mg dose) will be considered as study treatment throughout the study, which will be compared with placebo (two s.c. injections of 150 mg secukinumab matching placebo per dose).

The treatment groups and dosing frequency are described in Table 2-1 below:

**Table 2-1 Overview of study treatment**

Treatment group	DB Treatment Period (Rand – Wk 12 pre-dose)	DB Induction Period (Wk 12 – Wk 15)	OL Treatment Period (Wk 16 – Wk 52)
Secukinumab 300 mg	2x s.c. secukinumab 150 mg injection at Rand, Wks 1, 2, 3, 4 and 8	2x s.c. secukinumab 150 mg injection at Wk 12  2x s.c. secukinumab 150 mg PBO injection at Wks 13, 14 and 15	2x s.c. secukinumab 150 mg injection at Wks 16 – 48
Placebo (PBO)	2x s.c. secukinumab 150 mg PBO injection at Rand, Wks 1, 2, 3, 4 and 8	2x s.c. secukinumab 150 mg injection at Wks 12, 13, 14, and 15	2x s.c. secukinumab 150 mg injection at Wks 16 – 48

DB = Double-blind; OL = Open-label; Rand = Randomization; Wk = Week

### 2.1.1.2 Study day

The day of first administration of the double blind randomized treatment will be considered as study day 1. All other study day will be labeled relative to study day 1. The descriptor “study day 0” will not be used.

The day for a particular event on or after the study day 1 will be calculated as:

$$(\text{date of event}) - (\text{date of first dose}) + 1.$$

For example study day 2, study day 3... will be one day, two days... after study day 1, and respectively.

The day before study day 1 will be calculated as:

$$(\text{date of event}) - (\text{date of first dose}).$$

For example study day -1, study day -2,..., will be one day, two days,..., before study day 1 respectively.

### **2.1.1.3 Baseline and post-baseline assessments**

Baseline assessments are defined as the last assessment before the first dose of double-blind randomized study treatment, which is typically the last assessment taken before study drug administration at Visit 2. If the baseline assessments are missing, then the last available measurement before the first dose of study treatment will be considered as baseline.

All the assessments after first dose of study treatment will be considered as post -baseline assessments. Therefore, Visit 3 and later visits will be considered as post-baseline visit.

Any procedure performed between Visit 1 and Visit 2 will be considered as screening assessment.

#### **2.1.1.4 Day of last dose of randomized study treatment**

The date of last dose will be collected via the CRF.

Duration of exposure is defined in [Section 2.4.1](#).

If a subject discontinued early, then the last visit during the treatment period is considered (e.g., last visit in the induction period, if patient discontinued from the induction period) to calculate the duration of exposure.

On-treatment is defined as assessments within last dose plus 84 days.

## **2.2 Analysis sets**

The following analysis sets will be used for the statistical reporting and analyses:

**Randomized Set:** The randomized set includes all subjects who were randomized.

**Safety Set:** The Safety Set includes all subjects who received at least one dose of study medication. Subjects will be analyzed according to treatment received.

**Full Analysis Set:** The Full Analysis Set includes all subjects to whom study medication has been assigned. Subjects inappropriately randomized (e.g., IRT was called in error for randomization of a screen failed subject) will be excluded from this analysis set. Following the intent-to-treat principle, subjects will be analyzed according to the treatment they were assigned to at randomization.

Rule for exclusion criteria from analysis sets: See [Appendix 5-5](#).

## **2.3 Patient disposition, demographics and other baseline characteristics**

### **2.3.1 Patient disposition**

The number of subjects screened will be presented along with the reasons for screen failures for all subjects as specified in the screening phase disposition eCRF.

The number and percentage of subjects screened, randomized, completed study periods (treatment period 1 and treatment period 2), and discontinued the study prematurely including

the reason for discontinuation will be presented by overall and study periods for each treatment group for all screened subjects.

Patients withdrawing consent will be listed with reason for withdrawal.

The number and percentage of subjects with protocol deviations (see Appendix 5-5) will be tabulated by treatment and listed separately by treatment groups.

### **2.3.2 Demographics**

The following demographic data collected at Visit 2 will be summarized by treatment for the Full analysis set and the Randomized set:

- age (in years)
- sex (male/female)
- race (Caucasian/black/Asian/native American/pacific islander/unknown/other)
- ethnicity (non-Hispanic or Latino/Hispanic or Latino)
- Child-bearing potential (able to bear child/post-menopausal/sterile - of child bearing age).

### **2.3.3 Baseline characteristics**

The following baseline characteristics data will be summarized by treatment groups for the Full analysis set and the Randomized set:

#### **Psoriasis history / Prior psoriasis therapies**

Psoriasis history and prior psoriasis therapies collected at Visit 1 will be summarized by treatment group.

Duration of plaque psoriasis will be calculated as follows:

Date of Visit 1 – Date of first diagnosis of plaque psoriasis + 1.

This duration will be summarized descriptively.

The type of prior psoriasis therapy (biologic systemic therapy, non -biologic systemic therapy, topical, phototherapy, photochemotherapy) and the respective duration of exposures will be reported along with the reason of discontinuation of the therapy. This data will also be listed.

#### **Smoking history**

Smoking history collected at Visit 1 will be summarized by treatment in terms of estimated number of pack-years based on the approximate consumption per-year.

The subject's tobacco usage status (never, current, former) will be collected and frequency and percentage of different status will be presented by treatment.

Time since last date of tobacco use (for former category) will be calculated as follows:

Date of Visit 1 – Date of last use of tobacco + 1. This duration will be summarized descriptively by treatment.

### **Alcohol use history**

Alcohol use history will be summarized by treatment in terms of estimated number of alcoholic drinks consumed per day captured at Visit 1.

Time since last date of alcohol consumption will be calculated as follows:

Date of Visit 1 – Date of last alcohol consumption + 1.

This duration will be summarized descriptively by treatment.

### **Comorbidities – cardiovascular history**

Cardiovascular history will be summarized using frequencies and percentages by categories specified in the eCRF, ongoing status and treatment. Duration of cardiovascular diseases ongoing at Visit 1 will be summarized descriptively. Frequency and the percentage of the occurrence of each category will be presented. Also, frequency and percentage of ongoing cardiovascular disease will be presented. This data will also be listed.

In addition, family history of cardiovascular disease will be summarized descriptively. This data will also be listed.

### **Relevant medical history / Current medical conditions**

Relevant medical history / current medical conditions will include data up to six months prior to signing of the informed consent and not including psoriasis or psoriatic arthritis and cardiovascular histories. Any condition entered on the relevant medical history / current medical conditions CRF will be coded using the MedDRA dictionary and summarized by System Organ Class (SOC) and Preferred Term (PT). This data will also be listed with ongoing treatments flagged.

### **Tuberculosis status**

Presence of tuberculosis is assessed at Visit 1 which includes tuberculosis workup conducted (yes/no), result of workup (active, latent, no – tuberculosis diagnosed/present) and tuberculosis therapy started (yes/no). This data will be summarized by treatment.

### **Other baseline characteristics**

In addition, the following variables collected at baseline will be summarized by treatment:

- height (in cm)
- weight (in kg)
- pulse (beats/min)
- blood pressure (mmHg)
- hematology
- clinical chemistry
- viral serology

- HIV 1/2
- Hepatitis B
- Hepatitis C
- serum pregnancy
- PASI score
- IGA mod 2011 score
- DLQI total score

## **2.4 Treatments (study treatment, rescue medication, concomitant therapies, compliance)**

### **2.4.1 Study treatment exposure and compliance**

The duration of exposure to study treatments will be presented based on safety set.

Duration of exposure is defined as the time from first dose of study treatment to the time of treatment switch (for subjects who switch treatment) or end of treatment period. For subjects who discontinue duration of exposure will be the last visit in the corresponding treatment period. For example if a subject discontinues during induction period, this will be the discontinuation date from induction period recorded on the induction period completion CRF page.

Duration of exposure (days) = min (last study visit (including follow-up if applicable) date, last dose date +84) – first dose date +1

Duration of exposure (years) = duration of exposure (days) / 365.25

The duration in days will be summarized by treatment, descriptively and using frequencies and percentages for categories: “≥4 weeks”, “≥12 weeks”, “≥16 weeks”, and “≥52 weeks”.

More precisely, duration of exposure will be summarized for following categories:

“any exposure”, “≥1 week”, “≥2 weeks”, “≥3 weeks”, “≥4 weeks”, “≥8 weeks”, “≥12 weeks”, “≥16 weeks”, “≥28 weeks”, “≥40 weeks” and “≥52 weeks”.

Compliance as percentage of injections administered will be calculated as the number of injections applied (based on documented study drug administrations and syringe counts as given in the dosage administration record eCRF page) divided by the number of injections scheduled per protocol.

Compliance (%) = 100\*(total no of injections administered)/ (no. of injections prescribed).

Compliance to study treatment will be summarized descriptively and by categories:

<80% and 80% to 100%, by treatment.

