9.3 Treatments

The number of subjects and the length of time (in days) exposed to each treatment will be summarized for the Safety Set. Note that during the Double-blind Treatment Period, all subjects will receive their last dose of study treatment at Visit 7/Week 8.

Concomitant medications will be summarized by treatment using frequency counts and percentages for the Safety Set.

Any condition entered as medical history or current medical condition at baseline will be coded using the MedDRA dictionary for the Safety Set. They will be summarized by system organ class and preferred term of the MedDRA dictionary. Summaries for cardiovascular and psoriasis-specific medical history will be provided as well.

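### The exposure formula in SAP 2.4.1 omits the treatment switch that its own definition requires: reported under placebo, a placebo-arm Week 52 completer would get 365 days instead of about 84

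*SAP*

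**What the plan says.** SAP 2.4.1 gives two rules for the same quantity.

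- The definition: "Duration of exposure is defined as the time from first dose of study treatment to the time of treatment switch (for subjects who switch treatment"). Subjects who do not switch are counted to the end of the treatment period.
- The formula: "Duration of exposure (days) = min (last study visit (including follow-up if applicable) date, last dose date +84"), minus "first dose date +1". The result is also converted to years.

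The section adds a rule for subjects who stop early: "For subjects who discontinue duration of exposure will be the last visit in the corresponding treatment period". SAP 2.1.1.4 refers back to 2.4.1 and repeats that rule. Neither place adds a switch date for subjects who carry on.

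On reporting, the SAP states: "The duration in days will be summarized by treatment, descriptively and using frequencies and percentages for categories". The categories run up to 52 weeks or more. Protocol 9.3 asks for the same thing: "The number of subjects and the length of time (in days) exposed to each treatment will be summarized for the Safety Set".

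Under Protocol 5.2, all placebo subjects change to secukinumab from Week 12. SAP 2.8 names two reporting groups for the whole treatment period, Secukinumab 300 mg and a combined Placebo / Secukinumab 300 mg group. SAP 2.4.1 does not refer to them.

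**The concern.** A programmer will normally code the formula, because it is the only explicit calculation in the section. For a placebo subject who continues after Week 12, it keeps counting through the secukinumab phase to the last visit. Shown under placebo, that time would place subjects with 12 weeks of placebo in the rows for 16 weeks and longer.

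The opposite error follows as well. The formula starts at the first dose of study treatment, so it never isolates the secukinumab time of the placebo arm. The by-treatment summary that the protocol requires would then be wrong for placebo and incomplete for secukinumab.

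**Working it through.** **Inputs (scheduled days, first dose on the day of randomization)**

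| Item | Day | Source |
|---|---|---|
| First dose | 1 | SAP 2.1.1.2 |
| Last placebo dose, Week 8 | 57 | Protocol 3.1.2; SAP Table 1-1 |
| Switch, Week 12 | 85 | Protocol 5.2; SAP Table 1-1 |
| Last dose, Week 48 | 337 | Protocol 3.1.4; SAP Table 1-1 |
| Last visit, Week 52 | 365 | SAP Table 1-1 |

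**The plan's own figure.** Neither document states an expected exposure in days. Protocol 3.2 says that placebo subjects can receive up to 40 weeks of secukinumab. On these days, (365 − 85)/7 = 40.0 weeks, which agrees.

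**Placebo-arm completer, final summary**

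- Formula: min(365, 337 + 84) − 1 + 1 = min(365, 421) = 365 days.
- Definition: Day 1 to the day before the switch is 84 days, or 85 if the switch day is counted.
- Ratio: 365/84 = 4.35, or 365/85 = 4.29.

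**Sensitivity to visit timing.** The Week 52 visit may fall on Day 358 to 372 (±7 days). The Week 12 dose may fall between Day 83 (visit two days early) and Day 94 (visit two days late, dose seven days after the scan). The ratio then ranges from 358/94 = 3.8 to 372/82 = 4.5.

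**Subjects who stop after the switch.** Take a discontinuation visit 28 days after the last dose and compare with 85 days.

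| Last dose | Formula (days) | Ratio |
|---|---|---|
| Week 12 (Day 85) | 113 | 1.3 |
| Week 16 (Day 113) | 141 | 1.7 |
| Week 28 (Day 197) | 225 | 2.6 |

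**No overstatement.** With data cut at Week 12, the formula gives min(85, 57 + 84) − 1 + 1 = 85 days. Subjects who stop before switching have no secukinumab time to be miscounted.

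**Arm level (assumed dropout).** The sample size section allows 10% loss to follow-up but gives no timing.

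- 10% leaving at about Day 43: (0.9 × 365 + 0.1 × 43)/(0.9 × 85 + 0.1 × 43) = 332.8/80.8 = 4.1.
- 10% leaving at about Day 197: (0.9 × 365 + 0.1 × 197)/85 = 348.2/85 = 4.1.
- 20% at the same two times: 3.9 in both cases.

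With 42 subjects and no dropout, the placebo total is 42 × 365/365.25 = 42.0 person-years by the formula and 42 × 85/365.25 = 9.8 by the definition.

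**The case against.** The best defence is that the definition stands directly above the formula and already stops at the switch. On that view the error needs a programmer to ignore the adjacent sentence. This is fair as far as it goes: the misstatement is conditional, not certain. But the SAP does not say which rule prevails. The early-stopping rule does not help either, because it covers only discontinuers and ends at a visit, not at the switch.

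The second defence is SAP 2.8. If the exposure table used the whole-period groups there, 365 days would appear under Placebo / Secukinumab 300 mg and would correctly state total time on study treatment. This also stands, but it is only a plausible reading. Those groups sit under the safety analyses, and 2.4.1 does not cite them. The total would still not be the quantity that 2.4.1 defines, nor the exposure to each treatment that Protocol 9.3 requires.

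Three stronger readings are tempting, and the documents do not support them.

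- A reader might infer a fourfold error throughout. It applies to placebo-arm subjects who complete Week 52, in the final summary, if the time is labelled placebo.
- A reader might infer that placebo exposure in the first period could reach Day 57 + 84 = Day 141. That pairs a period-level last dose with a study-level last visit. With both restricted to the period, the Week 12 visit caps it at Day 85.
- A reader might infer that adverse event rates would be distorted. Exposure is converted to years, but neither document specifies an exposure-adjusted rate. Adverse events and serious adverse events are planned as numbers and percentages of subjects.

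**Conclusion.** The point holds as an inconsistency of specification within SAP 2.4.1, and nothing elsewhere resolves it. If the formula is applied literally at Week 52 and reported under placebo, a completer is credited with 365 days in place of 84 to 85. That is about 4.3 times too long on schedule, and 3.8 to 4.5 times within the permitted visit timing. The figures rest on study-level last visit and last dose dates and on a first dose on the day of randomization.

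The damage is limited to one descriptive Safety Set table: days, years and duration categories. The secukinumab arm is unaffected because it never changes drug. The matter is minor, but the table is one the protocol requires.

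**What to change.** For subjects randomized to placebo who switch, replace the single formula in SAP 2.4.1 with two:

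- Placebo exposure = min(last visit, last placebo dose + 84, first secukinumab dose − 1) − first placebo dose + 1. On schedule: min(365, 141, 84) − 1 + 1 = 84 days.
- Secukinumab exposure = min(last study visit, last secukinumab dose + 84) − first secukinumab dose + 1. On schedule: min(365, 421) − 85 + 1 = 281 days.

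The two parts sum to 365 days, so no day is lost or counted twice.

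Keep the existing formula for the secukinumab arm. State that its sham placebo injections at Weeks 13, 14 and 15 are not a switch. A general cap at the first dose of the next treatment would be unsafe, because read literally it could end secukinumab exposure at Week 13.

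If total time over the entire treatment period is also reported, label it Placebo / Secukinumab 300 mg as in SAP 2.8, not placebo.

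The cost is a few lines of SAP text and a small programming change, with no new data. One consequence should be expected: subjects who take the Week 12 dose a day or two early, as the visit window allows, will fall just below the row for 12 weeks or more.
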